10.4 DESCRIPTION OF STATISTICAL METHODS

10.4.1 GENERAL APPROACH

Using the Evaluable Dataset, all secondary endpoints will be summarized serially over time using descriptive statistics to assess the within-subject changes and between-group differences. Overall baseline and demographic data will be summarized using descriptive statistics.

For analysis of the primary and secondary endpoints, the following will be considered:

- For endpoints that are continuous in nature:
 - Number of observations, mean, median, minimum and maximum, and standard deviation (SD) values will be presented as descriptive summary
- For endpoints that are categorical in nature:
 - Frequency counts and percentages will be presented as descriptive summary

Subject disposition (e.g., the number of subjects randomized, completed, and discontinued) will be summarized, and medical history data will be listed. Prior and concomitant medications taken from Screening and during the study will be categorized by World Health Organization classification for therapeutic class and medication name, listed and summarized by number and percentage of subjects.

Final analyses are not limited to the summaries described herein. As noted above, analytical details and assumptions will be fully presented in the SAP.

10.4.2 ANALYSIS OF THE PRIMARY ENDPOINT

Safety and tolerability will be evaluated by examining the occurrence of TEAEs and AEs leading to de-escalation and/or discontinuation from the study.

Summary tabulations of the reported AEs will be presented by arm and column size after the verbatim terms have been coded to PTs and SOCs using the MedDRA Version 21.0 coding dictionary. The summaries will include severity and attribution to the study device. Multiple reports of the same AE by the same subject will be counted only once at the highest severity and strongest attribution to the study device.

Additional details are presented in [Section 10.4.4](#).

10.4.3 ANALYSIS OF THE SECONDARY EFFICACY ENDPOINTS

The study is not powered to detect significant changes in cognition, function, etc.; however, using available data from analysis of the secondary efficacy endpoints, including changes in scores from baseline, descriptive summaries will be developed. Of particular interest will be the within-subject changes from baseline and their distribution around a null value of zero and a comparison between groups to evaluate any trends in differences between subjects randomized to active vs. control.

10.4.4 ANALYSIS OF THE SECONDARY SAFETY ENDPOINTS

Actual values and changes from baseline in clinical laboratory measurements, vital signs, and body weight, will also be assessed and summarized. Laboratory shift tables or graphics displaying the change (number of subjects) relative to the reference range from baseline to each study visit may also be presented for each test. The investigator should exercise his or her medical and scientific judgment in deciding and documenting whether an abnormal laboratory finding or other abnormal assessment is clinically significant.

For secondary safety endpoints that are continuous in nature (e.g., clinical laboratory parameters, systolic and diastolic BP, heart rate, respiratory rate, body temperature, and body weight) the mean, median, minimum, maximum, and standard deviation will be summarized.

For secondary safety endpoints that are categorical in nature (e.g., physical examination or ECG abnormalities), the frequency counts and percentages will be presented as a descriptive summary.

Per-subject extent of exposure will be listed.

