5.4.2 HANDLING OF PARTICIPANT WITHDRAWALS/DISCONTINUATION

Subjects will be encouraged to complete the study and all assessments. Subjects may voluntarily withdraw at any time, and the investigator may discontinue individual subjects from the study at any time.

Approximately 26 subjects will be enrolled with the intent of obtaining 20 evaluable subjects randomized in a 1:1 ratio to either active (AKST1210 column) or control. Subjects who discontinue or are unblinded prior to Week 8 may be replaced.

Subjects who have received at least 1 HD with AKST1210/control but are withdrawn or withdraw from the study will be encouraged to complete the EOS procedures within 4 to 6 weeks of their last visit. The primary reason for study discontinuation will be documented on the case report form (CRF).

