5.2.3 Evaluable Population

The Evaluable population will consist of all subjects who completed through Week 8, defined as having a week 8 visit. All secondary endpoints will be summarized for the Evaluable population. Analysis will be done according to the treatment subjects were randomized to.

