5.7 Efficacy Analyses

Efficacy analyses will evaluate the feasibility of conducting expanded studies of AKST1210 in subjects with ESRD-CI who are undergoing HD 3 times per week, and its efficacy. The efficacy analyses will be descriptive only. Except where indicated, efficacy parameters will be summarized using the Evaluable and PP populations. All efficacy data, regardless of population, will be presented in data listings.

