5.7.8 Duration of Treatment Based on Column Size

The duration of treatment will be summarized by column size (AKST1210 S-15, S-25, and S-35), overall AKST1210 and control at baseline, and at each scheduled post-baseline time point. The duration of each HD session in hours, the number of days of HD session, and the total duration of HD session (hours) will be summarized in each treatment period.

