5.8.5.2 Summary for serious TEAEs

For all serious TEAEs the following will be summarized (included in DSMB report):

- Overall summary of any serious TEAEs by worst severity presented by SOC/PT
- Overall summary of any serious TEAEs by closest relationship presented by SOC/PT

A listing of all serious AEs will be provided. This listing will include a flag identifying if a serious AE is a TEAE.

A test of hypothesis comparing the proportions of subjects reporting a TEAE throughout the study will be conducted using a Chi-square or Fisher's exact test, as appropriate. The null hypothesis is that there is no difference in proportion between treatment groups, with a two-sided alternative that considers the possibility of a difference in either direction. The number and percentage of subjects reporting a TEAE and the 95% Wilson confidence interval (CI) for the proportion will be presented for each treatment group. In addition, the difference in proportions between the device and control groups and the 95% Wilson CI will be presented. The same statistics and hypothesis testing will be performed for subjects reporting a SAE throughout the study.

All *P* values will be displayed in four decimals and rounded using standard scientific notation (e.g., 0.XXX). If a *P* value less than 0.0001 occurs it will be shown in tables as <0.0001.

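### TEAEs and SAEs are compared only as crude proportions with no time at risk, and no exposure summary is specified for the Safety population that forms their denominator

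*Protocol*

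**What the plan says.** **Primary endpoint.** It is the incidence of TEAEs and SAEs. Protocol 10.4.2 states: "Safety and tolerability will be evaluated by examining the occurrence of TEAEs and AEs leading to de-escalation and/or discontinuation from the study". It adds tabulations by arm and column size.

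**Comparison between arms.** SAP 5.8.5.2: "A test of hypothesis comparing the proportions of subjects reporting a TEAE throughout the study will be conducted", by Chi-square or Fisher's exact test with Wilson intervals, and likewise for SAEs. Where SAP 5.8.5 speaks of incidence rates, it means counts and percentages. Neither document gives a person-time rate or a time-to-event method for adverse events.

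**Exposure.** Protocol 10.4.4: "Per-subject extent of exposure will be listed". SAP 5.8.4 lists device accountability without summarising it. SAP 5.7.8 does provide a summary: "The duration of treatment will be summarized by column size (AKST1210 S-15, S-25, and S-35), overall AKST1210 and control at baseline" and at later time points. In addition, the length of each session, "the number of days of HD session, and the total duration of HD session (hours) will be summarized in each treatment period".

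**Population.** SAP 5.7.8 names none of its own, so the rule in SAP 5.7 applies: "Except where indicated, efficacy parameters will be summarized using the Evaluable and PP populations". SAP 5.2.3 adds: "The Evaluable population will consist of all subjects who completed through Week 8, defined as having a week 8 visit". The safety analyses use everyone with at least one study session after randomization (SAP 5.2.2).

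**Follow-up.** Completers have their EOS visit at Day 96, 14 days after the Day 82 end-of-treatment session (Protocol 15.1.5). After an early stop, EOS procedures are due unless consent is withdrawn (Protocol 5.4.1, 7.3.4). Such subjects "will be encouraged to complete the EOS procedures within 4 to 6 weeks of their last visit" (Protocol 5.4.2).

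**The concern.** A proportion ever affected depends on how long subjects are watched. Here that time need not be equal between arms. The plan allows for 20% drop-out, and Protocol 10.4.5 accepts that adherence may vary by arm. The IDH and hemoglobin stopping rules apply to both arms, but a stop caused by the column can arise only with AKST1210. Stops before Week 8 may be replaced (Protocol 5.4.2), in the same arm (SAP 4.5.1), so an arm with many early stops can also gain subjects with short follow-up in its Safety denominator.

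If this happens, the percentages for SAEs and for events unrelated to the stop are too low in the arm with more stops. A reader of the tables could not see by how much, because the one exposure summary leaves out the subjects responsible. In a largely descriptive study these percentages are the main safety result.

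The same problem arises by design if adverse events are shown by column size: each size is scheduled for 4 weeks, against 12 weeks of treatment for control.

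**Working it through.** **1. The plan's own figure.** 10 evaluable per arm / (1 − 0.20) = 12.5, rounded up to 13, so 26 in total; 26 × 0.80 = 20.8, or about 20 evaluable. This reproduces. No event rate or drop-out by arm is stated.

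**2. Inputs.** From the documents: n = 13 per arm (26 at 1:1), full follow-up T = 96/7 = 13.71 weeks, EOS 4 to 6 weeks after an early stop. Assumed: the same constant hazard in both arms, a 30% event over full follow-up, k = 3 or 5 AKST1210 subjects stopped at Week 4, no control stops, and stopping unrelated to the event counted. Follow-up f in stopped subjects is then 4 weeks (consent withdrawn at the stop), or 8 or 10 weeks (EOS 4 or 6 weeks later).

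**3. Formulas.**
- Hazard: λ = −ln(1 − 0.30)/13.71 = 0.0260 per week.
- Proportion affected within f weeks: q(f) = 1 − exp(−λf), giving 9.9% at 4 weeks, 18.8% at 8 and 22.9% at 10.
- Shortfall: (k/13) × (0.30 − q(f)).

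**4. Results for a 30% event** (control reads 30.0% throughout)

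| Stopped | Follow-up in stopped | AKST1210 crude | Shortfall (points) |
|---|---|---|---|
| 3 of 13 | 10 weeks | 28.4% | 1.6 |
| 3 of 13 | 8 weeks | 27.4% | 2.6 |
| 5 of 13 | 10 weeks | 27.3% | 2.7 |
| 5 of 13 | 8 weeks | 25.7% | 4.3 |
| 3 of 13 | 4 weeks | 25.4% | 4.6 |
| 5 of 13 | 4 weeks | 22.3% | 7.7 |

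With EOS done the range is 1.6 to 4.3 points; without it, 4.6 to 7.7. One subject in 13 is 7.7 points. If k/13 is the same in both arms with the same follow-up, both percentages fall equally and the difference is not biased.

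**5. What person-time does.** Events divided by subject-weeks to first event or end of follow-up gives 0.0260 per week in both arms in every row, because the hazards were set equal.

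**6. Later stops.** A stop at Week 8 with EOS 4 weeks later gives f = 12 and q = 26.8%. The shortfall with 5 stops is (5/13) × 3.2 = 1.2 points.

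**7. Column size.** At the same hazard, a 4-week column-size period would read 9.9% beside 30.0% for a control column covering the whole study.

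**The case against.** **Exposure is summarised.** A reader of Protocol 10.4.4 alone might infer that exposure is only listed. SAP 5.7.8 shows otherwise. What remains is that its default populations do not match the adverse event denominator. The hemodialysis tables in SAP 5.8.1 do use the Safety population by visit, so their counts hint at attendance, but they give no time at risk.

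**Harm-driven stops do not make the any-TEAE percentage fall.** A reader might infer that the more subjects the column forces off study, the safer it looks. The documents do not support this for any TEAE. Every IDH after consent is an adverse event (Appendix 17.1), and the IDH rule requires several, so a subject stopped under it is already in the numerator. Clinically significant laboratory values are adverse events too (Protocol 7.2.1). If 3 to 5 stopped subjects all count and 60% of the others do, the arm reads (3 + 10 × 0.60)/13 = 69% to (5 + 8 × 0.60)/13 = 75%, above 60%. This stands, and confines the bias to SAEs, other event terms and stops not caused by adverse events.

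**Such stops are visible elsewhere.** TEAEs leading to withdrawal, disposition with reasons, and discontinuation reasons by arm are all planned (SAP 5.8.5.3, 5.3; Protocol 10.4.5). This also stands. Those tables show that subjects left, but do not correct the SAE percentage.

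**The size is small and conditional.** With the EOS visit the shortfall is under one subject per arm, and the absence of control stops is an assumption. The tests are weak anyway: Fisher power is about 0.26 for 30% against 60% with 13 per arm. So the effect is on the estimates rather than on a decision.

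**Conclusion.** The point holds in a limited form. The between-arm safety comparison takes no account of time at risk, and no exposure summary is specified for the subjects it counts. Whether this biases anything depends on early stopping differing by arm, which the documents neither project nor rule out. Under the stated assumptions the understatement for a 30% event is 1.6 to 4.3 points when EOS is done and at most 7.7 when consent is withdrawn at the stop. The upper figure needs five stops at Week 4 in one arm, none in the other and no later follow-up, so it is a bound and not an expectation. The documents do not support a general claim that the column will look safer than it is. The change is worth making because it costs little.

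**What to change.** Keep the crude proportions and the per-subject exposure listing. Then:

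- Add a Safety-population table of weeks at risk and number of study sessions by arm, and by column size wherever adverse events are tabulated that way under Protocol 10.4.2.
- In SAP 5.8.5 and 5.8.5.2, add for any TEAE and any SAE the number of subjects with a first event per subject-week, from first study session to first event or end of adverse event follow-up, by arm, with the rate ratio and exact 95% CI. Rates for every SOC and PT are not needed at about 13 per arm.
- Use all adverse event follow-up in the main version. As a sensitivity version only, end follow-up 14 days after the last study session in everyone, which matches the completers' EOS interval. This version equalises the off-treatment time but drops later SAEs in early stoppers, so it should not be the main one.

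The cost is SAP wording and some programming from dates already collected. Footnote two limits: the rate is assumed constant although column size can change every 4 weeks, and person-time does not remove bias from stopping that is related to the risk of the event.

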10.4.5 ADHERENCE AND RETENTION ANALYSES

Subject adherence with the study visits schedule, visit procedures, HD procedures, and subject retention will be assessed. Subject adherence may vary across the treatment arms. Reasons for study discontinuation will be compared across treatment arms and across other subgroups of interest, as appropriate.

10.4.6 BASELINE DESCRIPTIVE STATISTICS

See [Section 10.4.1](#).

10.4.7 PLANNED INTERIM ANALYSES

Not applicable.

10.4.8 ADDITIONAL SUBGROUP ANALYSES

Not applicable.

10.4.9 MULTIPLE COMPARISON/MULTIPLICITY

No adjustments for multiplicity will be employed.

10.4.10 TABULATION OF INDIVIDUAL RESPONSE DATA

This will be further defined in the SAP.

10.4.11 EXPLORATORY ANALYSES

Not applicable.

10.5 SAMPLE SIZE

Approximately 26 male and female subjects, ≥ 40 years of age on HD with ESRD-CI, will be enrolled. Assuming a drop-out rate of 20%, enrollment at this level will yield approximately 20 evaluable subjects (evaluable is defined as completed through Week 8). Subjects will be randomized in a 1:1 ratio consisting of 1 treatment arm (AKST1210) and 1 non-active, control arm; $n=10$ per group. The sample size was chosen based on clinical considerations of an exploratory study designed to test safety and tolerability (Thabane 2010).

While the study is not statistically powered to detect differences in measures of clinical efficacy or biomarker endpoints, the proposed sample size may be sufficient to identify trends in efficacy endpoints that will be used to determine the appropriate sample size for subsequent studies.

10.6 MEASURES TO MINIMIZE BIAS

10.6.1 ENROLLMENT/RANDOMIZATION/MASKING PROCEDURES

To minimize the potential bias at the time of randomization, the study will be double-blinded (the subject, investigator, and outcomes assessor will be blinded as to treatment assignment and randomized in a 1:1 ratio [AKST1210: control]). The randomization codes will be generated by a statistician that has no involvement in the study other than generation and maintenance of the randomization codes. Blinding and randomization procedures are described in the Device Procedures Manual.

10.6.2 EVALUATION OF SUCCESS OF BLINDING

Success of blinding will be assessed based on all occurrences (intentional or unintentional) of unblinding of blinded study subjects, or study personnel (e.g., investigators, medical providers, outcomes assessors, the

Sponsor or their representatives). All intentional and unintentional unblinding will be documented and reported.

10.6.3 BREAKING THE STUDY BLIND/SUBJECT CODE

This is a double-blind study. Blinding procedures are described in the Device Procedures Manual.

If unintentional unblinding occurs during the study, root cause analysis will be evaluated, and corrective actions implemented as applicable.

11 SOURCE DOCUMENTS AND ACCESS TO SOURCE DATA/DOCUMENTS

Each participating site will maintain appropriate medical and research records for this trial, in compliance with ICH E6 R2 and regulatory and institutional requirements for the protection of confidentiality of subjects. Each site will permit authorized representatives of regulatory agencies, the IRB, the Sponsor, or the Sponsor's representatives to examine (and when permitted by applicable law, to copy) clinical records for the purposes of quality assurance reviews, audits, and evaluation of the study safety, progress, and data validity.

Source data are all information, original records of clinical findings, observations, or other activities in a clinical trial necessary for the reconstruction and evaluation of the trial. Examples of these original documents and data records include, but are not limited to, hospital records, clinical and office charts, laboratory notes, memoranda, subject's memory aids or evaluation checklists, pharmacy dispensing records, recorded audio tapes of counseling sessions, recorded data from automated instruments, copies or transcriptions certified after verification as being accurate and complete, microfiches, photographic negatives, microfilm or magnetic media, x-rays, and subject files and records kept at the pharmacy, at the laboratories, and medico-technical departments involved in the clinical trial.

It is not acceptable for the CRF to be the only record of a subject's participation in the study. This is to ensure that anyone who would access the subject's medical record has adequate knowledge that the subject is participating in a clinical trial. Source document templates will be developed for this study.

12 ETHICS/PROTECTION OF HUMAN SUBJECTS

12.1 ETHICAL STANDARD

The investigator will ensure this study is conducted in full conformity with Regulations for the Protection of Human Subjects of Research codified in, 21 CFR Parts 11,50, 54, 56, 812, ICH E6 R2, and the Declaration of Helsinki.

12.2 INSTITUTIONAL REVIEW BOARD

This protocol and any accompanying material to be provided to the subject (such as advertisements, subject information sheets, or descriptions of the study used to obtain informed consent) will be submitted by the investigator to an IRB. Approval from the IRB must be obtained before starting the study and should be documented in a letter to the investigator specifying the protocol number, protocol version, documents reviewed, and date on which the committee met and granted the approval.

All changes to the consent form will be IRB approved; a determination will be made regarding whether

previously consented subjects need to be re-consented.

Any amendments to the protocol must also be submitted to the IRB for approval prior to implementation.

If the investigator were to receive withdrawal of IRB approval, or other action on the part of the IRB that affects the study, the investigator will provide written notification within 5 days of the IRB decision to the Sponsor. If Alkahest were to receive withdrawal of IRB approval, or other action on the part of the IRB that affects the study, the Sponsor will provide written notification within 5 days of the IRB decision to the FDA and investigators.

12.3 INFORMED CONSENT PROCESS

12.3.1 CONSENT FORMS

Consent forms describing in detail the study device, study procedures, and risks are given to the subject or subject's LAR and written documentation of informed consent is required prior to any study-related procedures.

12.3.2 CONSENT PROCEDURES AND DOCUMENTATION

It is the responsibility of the investigator or designee to obtain written informed consent from each subject participating in this study or their legally authorized representative after adequate explanation of the aims, methods, objectives, and potential hazards of the study and prior to undertaking any study-related procedures.

Subjects should have the opportunity to discuss the study with their family members or other advisors and the time to consider participation in the trial carefully. The subjects may withdraw consent at any time throughout the course of the trial. The rights and welfare of the subjects will be protected by emphasizing to them that the quality of their medical care will not be adversely affected if they decline to participate in this study.

The investigator or designee must utilize an IRB-approved consent form that contains the elements required by ICH GCP and applicable regulatory requirements for documenting written informed consent. Each informed consent will be appropriately signed and dated by the subject and/or their legally authorized representative and the person obtaining consent. A copy of the signed consent form will be provided to the subject and/or their legally authorized representative. By signing the informed consent form, all parties agree they will complete the evaluations required by the study, unless they withdraw voluntarily or are terminated from the study for any reason.

Investigators will be expected to maintain a screening log of all potential study candidates that includes limited information about the potential candidate (e.g., date of Screening).

All subjects who provide consent will be assigned a unique study number. This number will be used to identify the subject throughout the clinical study and must be used on all study documentation related to the study subject. Once a number is assigned to a subject, that number will remain with that study subject and will not be reused.

If an individual's medical chart or results of diagnostic tests performed as part of an individual's regular medical care are going to be used for Screening, written informed consent must be obtained prior to review of that information in accordance with the Health Insurance Portability and Accountability Act (HIPAA).

